- A summary table presenting the number and proportion of subjects who lose at least 150mL and subjects who lose at least 200 mL of subcutaneous fat volume over the treated area together with two-sided Clopper-Pearson 95% confidence intervals for each treatment group defined in section 3.7 will be produced.
- For the subcutaneous fat volume as measured by ultrasound data, summary statistics (as described in section 3.1) will be presented for values and change from baseline value at each visit.
- If the assumptions met, the Mixed-Effect Model Repeated Measurement (MMRM) will be used to assess the change over time in the CBL-514 and placebo treatment arms for the abdominal subcutaneous fat volume. The assumptions for MMRM can be checked as described in section 16.3. There will not be any alternative method used if assumptions of model-based analysis are not satisfied.

The model will include the following fixed factors/covariates:

- o Baseline subcutaneous fat volume,
- o Treatment Group,
- o Study Visit,
- o Treatment Group and Study Visit interaction term;

Subject as random effect and repeated visits will be also included in the model.

Unstructured within-subject covariance structure (TYPE=UN) will be selected for the model initially which makes no assumption about the relationship in the correlation among visits. If it leads to non-convergence, the following covariance structures will be explored: first order autoregressive (AR (1)), Heterogenous Toeplitz, Toeplitz, and compound symmetry, if appropriate. If the model does not converge, alternative covariance structures will be investigated. The Akaike Information Criteria (AIC) will be used to select the best model (smaller is better).

If model does not converge after the above, a standard regression model will be fitted at each time point using the same covariates as described above.

The Kenward-Roger (Kenward and Roger 1997) approximation will be used to estimate denominator degrees of freedom for tests of fixed effects.

Also, if the model is complex, simpler model will be explored.

The LS mean change from baseline, along with corresponding 95% CI and p-values for each treatment arm for Visit 3, Visit 4, Visit 5, Visit 6, and Visit 7 will be presented. In addition, the difference in change from baseline at Visit 6 and Visit 7 for CBL-514 600 mg versus placebo will be provided for the ITT population and repeated for PP Population.

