16.3 Appendix 3: MMRM Assumptions Testing

a) Sphericity assumption

The first assumption of the MMRM analysis is sphericity, posits that the repeated measures of a within-subjects effect should have equal variances and constant covariances.

- When the sphericity assumption is satisfied, the F-test in a standard analysis of variance is appropriate.
- When the sphericity assumption is violated, the F-test in a standard analysis of variance will be positively biased; that is, it will be more likely to make a Type I error (i.e., reject the null hypothesis when it is, in fact, true).
- Violation of sphericity was corrected using the Greenhouse–Geisser method.

b) Normality assumption

Kolmogorov-Smirnov normality test will be used to check normality of the data and the results will be presented.

SAS Proc to be used for normality testing:

```
ods output TestsForNormality = Normal;
proc univariate data=input normal plots;
var CFB; *CFB=Change from baseline;
histogram Diff /normal;
qqplot /normal (mu=est sigma=est);
run;
ods output close;
data Normality;
set Normal (where = (Test = 'Kolmogorov-smirnov'));
if pValue > 0.05 then Status = "Normal";
else Status = "Non-normal";
drop TestLab Stat pType pSign;
run;
```

Perform the following steps to check the normality of data.

1. First, check normality of data by pooling all visits data together if normality is achieved perform the parametric test.
2. If overall data doesn't show normality, check normality at each timepoint and if only few timepoints achieve normality, then still perform parametric test as normality can be assumed for non-normal timepoint.
3. If extreme outliers are present, then remove the outliers and check normality to perform parametric test.
4. Other normality tests result will be explored in case of departure from normality assumption.
5. If normality assumption is still violated, the normality will be assumed to perform parametric tests.

c) Test for Homoscedasticity

Homogeneity of variances between two treatment groups will be tested using Levene's test.

```
proc glm;  
class treat;  
model CHG = treat;  
means treat / hovtest=levene welch;  
  
run;
```

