Note that only the results from the HOVTEST= and WELCH options in PROC GLM account for variance heterogeneity. All other results assume equal variances. If heteroscedasticity occurs, all the results will be adjusted for unequal variances by adding the DDFM=SATTERTHWAITTE option in the MODEL statement to adjust the degrees of freedom for the unequal variances.

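### SAP Appendix 3 checks the MMRM's normality and equal-variance assumptions on raw change from baseline, not on model residuals, so the checks can fail when the assumptions hold

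*SAP*

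**What the plan says.** SAP Section 10 makes the Stage 2 model conditional: "If the assumptions met, the Mixed-Effect Model Repeated Measurement (MMRM) will be used to assess the change over time". It adds that nothing replaces the model if its assumptions fail. The model has baseline volume, arm, visit and arm-by-visit as fixed terms, an unstructured covariance over visits that is common to both arms (the sample code has no `GROUP=`), and Kenward-Roger degrees of freedom.

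The checks are in SAP 16.3, Appendix 3.

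- **Normality, 16.3(b).** The Kolmogorov-Smirnov (KS) test is run on "var CFB; *CFB=Change from baseline", with no class or by-group. Step 1: "First, check normality of data by pooling all visits data together if normality is achieved perform the parametric test". Step 2, if that fails: "check normality at each timepoint and if only few timepoints achieve normality", the parametric test still goes ahead. Step 3: "If extreme outliers are present, then remove the outliers and check normality to perform parametric test". Step 5 assumes normality if everything else has failed.
- **Equal variance, 16.3(c).** "Homogeneity of variances between two treatment groups will be tested using" Levene's test, coded in PROC GLM as "model CHG = treat", with no visit term and no BY visit. The action is: "If heteroscedasticity occurs, all the results will be adjusted for unequal variances", by switching the degrees-of-freedom option to Satterthwaite.

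**The concern.** An MMRM assumes normal residuals with the same covariance in each arm, after the fixed terms are removed and with visits correlated within subject. Raw change contains those fixed effects. When visits are pooled, the movement of the CBL-514 mean from Visit 3 to Visit 7 counts as variance in that arm. When arms are mixed, the gap between them counts as non-normality. Five correlated values per subject are treated as independent, which disturbs both tests even if the drug does nothing.

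At stake is the only between-arm estimate that Section 10 specifies for Stage 2, the difference in volume change at Visits 6 and 7. Its degrees-of-freedom method, the normality results reported beside it and, on the literal wording of Section 10, whether it is reported at all would depend partly on how well the drug works.

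**Working it through.** **Inputs from the documents.** Protocol synopsis, Table S3: 50 and 25 randomized, drop-out 16% and 44%. Reproducing the plan's figure: 50 × 0.84 + 25 × 0.56 = 42 + 14 = 56 evaluable. Section 10 reports five post-baseline visits (3 to 7), so complete data give 56 × 5 = 280 values. The 150 and 200 mL effects used below are the trial's own responder thresholds.

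**Assumptions, because the documents give none.** SD 60 to 100 mL; within-subject correlation 0.5 to 0.8; placebo mean change 0; CBL-514 mean change reaching 25, 50, 75, 100 and 100% of its final size D over Visits 3 to 7; a 5% level for Levene (the SAP states 0.05 only for normality).

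**Why Levene is disturbed.** The visit fractions have mean 0.70 and variance (0.2025 + 0.04 + 0.0025 + 0.09 + 0.09)/5 = 0.085. Pooled over visits, the CBL-514 variance is therefore σ² + 0.085 D², not σ². At D = 2σ the SD is inflated by √1.34 = 1.16; at D = 3σ by √1.765 = 1.33.

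**False failures.** The simulated data are normal with equal covariance in both arms, 42/14 subjects. Entries are % rejected.

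| Check (correlation) | D = 0 | 1 SD | 1.5 SD | 2 SD | 3 SD | 4 SD |
|---|---|---|---|---|---|---|
| Levene as coded (0) | 4 | 6 | 13 | 26 | 80 | 100 |
| Levene as coded (0.5) | 17 | 16 | 23 | 37 | 78 | 99 |
| Levene as coded (0.8) | 34 | 35 | 37 | 47 | 74 | 97 |
| KS, visits and arms pooled (0.5) | 6 | 6 | 5 | 6 | 19 | 66 |
| KS, visits and arms pooled (0.8) | 20 | 16 | 14 | 10 | 25 | 71 |
| KS at Visit 7, arms mixed (0.5) | 3 | 3 | 6 | 14 | 50 | 94 |
| Levene on residuals, Visit 7 (0.5) | 6 | 6 | 5 | 6 | 5 | 6 |
| KS on scaled residuals (0.5) | 3 | 3 | 4 | 2 | 3 | 3 |

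With 1,000 trials the simulation standard error is at most √(0.25/1,000) = 1.6 points. Repeated runs put the no-effect Levene rate at about 14 to 32%, and the 34% above is within error of that.

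In mL, over correlations 0.5 to 0.8, Levene as coded rejects as follows:

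- 150 mL effect: 25–36% at SD 100, 38–45% at SD 75, 61–63% at SD 60.
- 200 mL effect: 39–48% at SD 100, 66–69% at SD 75, 87–91% at SD 60.

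The two causes separate. With independent visits and no effect, Levene holds its level (4%); correlation alone raises it to 17–34%. Pooled KS is moved mainly by correlation and by effects of about 3 SD or more.

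**Masking.** Let the placebo SD be 1.5 times the CBL-514 SD, so the true variance ratio is 1.5² = 2.25. With D = 200 mL, the ratio that Levene sees is:

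- SD 60 (D = 3.33 SD): 2.25/(1 + 0.085 × 11.11) = 2.25/1.94 = 1.16
- SD 100 (D = 2 SD): 2.25/1.34 = 1.68

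At correlation 0.5, simulated detection is about 20% and 67%, against about 82–84% for a check with one residual value per subject. If CBL-514 is the more variable arm (1.33 times, 42/14), detection by Levene as coded rises from 72% with no effect to 90% at 200 mL and 98% at 300 mL (SD 100 in the less variable arm): the difference is exaggerated, not hidden.

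**The case against.** The strongest reply is that little follows from a failed check. Step 2 goes ahead if only a few timepoints pass, and step 5 assumes normality regardless. A Levene failure changes only the degrees-of-freedom option. Section 10 says no claim can rest on the p-values, the protocol plans no formal testing, and the primary responder proportions with Clopper-Pearson intervals do not use these checks. The code also looks partly illustrative: PROC GLM names no dataset, the histogram variable is not the one analysed, and step 2 needs a by-visit run that the code lacks. That Levene pools visits is read from the code; the prose is silent. All of this stands and limits the weight of the point. It does not make raw changes a test of residual assumptions, and the visit pooling in normality step 1 is explicit in the prose.

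A reader might infer more than the documents support:

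- **That masking inflates type I error.** If placebo SD is 1.5 times larger, a common-variance Visit 7 comparison has a type I error of roughly 10–11%. The check does not cause this. A correct detection would still trigger only a degrees-of-freedom change, while the model keeps one covariance for both arms.
- **That any working drug makes both checks fail.** Levene is clearly affected from about 1.5 to 2 SD; pooled KS hardly moves below about 3 SD.
- **That real variance differences are hidden in general.** This needs placebo to be the more variable arm. Investigator-adjusted dosing between 300 and 600 mg and a variable number of courses make the opposite plausible.
- **That mixing arms leads to responders being removed as outliers.** The SAP does not define extreme. Taking it as beyond 3 interquartile ranges, at most 0.3% of simulated trials with a 200 mL effect (SD 50 to 200) had such a value, against 0.2–0.8% with no effect.

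**Conclusion.** The point holds in a limited form. The checks in 16.3(b) and (c) do not test the MMRM's assumptions. With variances truly equal, Levene as coded rejects about 14–32% of the time with no effect and about 40–90% with a 200 mL effect (SD 100 to 60), where 5% is intended. These sizes rest on assumed SDs, effects, visit profile, correlation and complete data; the inflation with no effect needs only correlated visits.

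The consequences are a data-dependent move from Kenward-Roger to Satterthwaite, misleading reported normality results, and a conflict over what a failure means: Section 10 read literally drops the MMRM, whereas step 5 and the end of 16.3(c) carry on. The analysis concerned is secondary and exploratory, and the primary endpoint is untouched. This should be corrected before the final analysis, but it does not threaten the trial's main result.

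**What to change.** 1. **Normality.** Use residuals from the fitted Section 10 MMRM, scaled by the estimated covariance, with Q-Q plots and the test. Delete step 1 and the arm-mixed form of step 2.
2. **Equal variance.** Run Levene on MMRM residuals by visit, or on one mean squared residual per subject. Centring on arm-by-visit means while still pooling visits is not enough: it rejected 16–19% under equal variances at correlation 0.5. If tests are by visit, use 0.01 for each of the five: at 0.05 each, some visit fails in about 18–26% of trials with equal variances; at 0.01, about 4–6%.
3. **Response to unequal variances.** A degrees-of-freedom option does not correct a common-covariance standard error. Specify an arm-specific covariance (`GROUP=treat` on the REPEATED statement), keep Kenward-Roger, and name a simpler structure in case of non-convergence. An unstructured matrix has 5 × 6/2 = 15 parameters per arm, against 14 evaluable placebo subjects.
4. **Consequence.** Reconcile the Section 10 condition with step 5 and 16.3(c) so that the MMRM is always reported, with the check results beside it.

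The cost is SAP wording and a few lines of SAS, with no new data. The downsides are limited power of by-visit variance tests with 14 placebo subjects (about 48% for a 1.5-fold SD ratio, about 40% with absolute deviations) and less stable arm-specific covariance estimates.

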No claim can be made on these p-values based on this efficacy analysis as it is exploratory in nature. These p-values should be used wisely.

The SAS code sample that can be used to implement the above MMRM analysis is given below:

```
PROC MIXED DATA= input_data;
CLASS treat (ref= 'Placebo') visit (ref='Baseline') usubjid;
MODEL chg= base treat visit treat*visit /ddfm=kr Solution CL;
REPEATED visit/subject=usubjid type=UN;
LSMEANS treat*visit/pdiff CL alpha=0.05;
LSMENAS visit/cl;
ods output lsmeans=lsmeans diffs=diffs;
run;
```

- The initial visits during which a subject experience a subcutaneous fat volume loss of 150 mL or more will be marked as flagged. For each subject, the number of treatments administered until the first flagged visit will be recorded and summarized descriptively along with the number of injections, volume and dose administered in accordance with Section 3.1. In cases where the subject is scheduled to receive the study treatment on the same date as the first flagged visit, that treatment will not be included in the count.

All the summary and analysis tables will be done for ITT and PP population for treatment groups defined in section 3.7.

All analyses will be performed without adjustment for multiple endpoints.

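### SAP Appendix 16.3(c) promises MMRM results adjusted for unequal arm variances, but the option it adds sets only degrees of freedom and leaves the standard errors pooled

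*SAP*

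**What the plan says.** SAP Section 10 analyses Stage 2 fat-volume change with an MMRM. Its sample code has "MODEL chg= base treat visit treat*visit /ddfm=kr Solution CL" and "REPEATED visit/subject=usubjid type=UN". The text names Kenward-Roger as the degrees-of-freedom method. If the unstructured matrix fails to converge, AR(1), heterogeneous Toeplitz, Toeplitz and compound symmetry are tried. After that, "If model does not converge after the above, a standard regression model will be fitted at each time point using the same covariates". None of these steps lets the variance differ by arm, and no robust standard error is specified.

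The model reports "The LS mean change from baseline, along with corresponding 95% CI and p-values for each treatment arm" at Visits 3 to 7, and the between-arm difference at Visits 6 and 7.

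Appendix 16.3(c) compares the arm variances with Levene's test in PROC GLM. It then says: "Note that only the results from the HOVTEST= and WELCH options in PROC GLM account for variance heterogeneity. All other results assume equal variances". The next sentence gives the remedy: "If heteroscedasticity occurs, all the results will be adjusted for unequal variances by adding the DDFM=SATTERTHWAITTE option in the MODEL statement". That sentence ends by saying the purpose is to adjust the degrees of freedom.

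**The concern.** Unequal arm variances are a problem of the standard error first and of the degrees of freedom second. The DDFM option acts only on the second. With one covariance matrix for both arms, each arm's standard error is built from a variance averaged over both. The option also displaces the Kenward-Roger method that Section 10 specifies, with no acknowledgement of the conflict. Results could then be described as adjusted for unequal variances when they are not.

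This MMRM gives the only planned between-arm estimate of fat-volume change, and the CBL-514 arm's own intervals, which serve the within-arm secondary endpoint. Stage 2 doses range from 300 to 600 mg per treatment, so a more variable CBL-514 arm is plausible; that is an inference, not something the documents state. The between-arm interval would then be too wide and the CBL-514 arm's interval too narrow. If placebo were the more variable arm, the between-arm interval would be too narrow.

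Three smaller points sit in the same appendix:

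- Nothing defines when heteroscedasticity has occurred, and the Levene code has no visit term.
- Step 3 of 16.3(b) mentions removing extreme outliers without defining them. It can be read as removing them from the MMRM or only from the normality check.
- Step 5 of 16.3(b) goes ahead whatever the normality result, while Section 10 makes the MMRM conditional on its assumptions and adds: "There will not be any alternative method used if assumptions of model-based analysis are not satisfied".

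**Working it through.** **Inputs.** Allocation 50/25 and dropout of 16% and 44% (SAP 2.5; Protocol Synopsis). Two-sided 95% intervals (SAP Section 10). The documents give no SDs, so the ratio r = SD(CBL-514)/SD(placebo) is an assumption, taken from 0.5 to 3.

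**1. The plan's own figure.** 50 × (1 − 0.16) = 42 and 25 × (1 − 0.44) = 14, total 56. This reproduces the planned evaluable number.

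**2. Pooled against correct standard error.** With complete data and ignoring the baseline covariate, at one visit and with placebo SD = 1:

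- pooled variance s² = [(n₁ − 1)r² + (n₂ − 1)] / (n₁ + n₂ − 2)
- pooled SE of the difference = √[s²(1/n₁ + 1/n₂)]
- correct SE of the difference = √(r²/n₁ + 1/n₂)
- pooled/correct SE of the CBL-514 mean = s/r

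Example, 42/14 and r = 2: s² = (41 × 4 + 13)/54 = 3.278. Pooled SE = √(3.278 × 0.09524) = 0.559. Correct SE = √(4/42 + 1/14) = 0.408. The ratio is 1.369. For the CBL-514 mean, √3.278/2 = 0.905.

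Pooled SE divided by correct SE:

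| r | Difference, 42/14 | Difference, 50/25 | CBL-514 mean, 42/14 | CBL-514 mean, 50/25 |
|---|---|---|---|---|
| 0.5 | 0.728 | 0.814 | 1.31 | 1.41 |
| 1.5 | 1.219 | 1.139 | 0.931 | 0.904 |
| 2 | 1.369 | 1.228 | 0.905 | 0.868 |
| 3 | 1.536 | 1.318 | 0.887 | 0.841 |

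**3. Degrees of freedom.** In this simplified setting the Satterthwaite df of the pooled-model contrast is n₁ + n₂ − 2, that is 54 or 73, at every r. The fitted model has only one covariance matrix, so even the df do not respond to unequal variances. Welch-type df at 42/14 would be 15.2 at r = 0.5 and 45.3 at r = 2. Attaching Welch df to the pooled SE does not repair it: at r = 0.5 and 42/14 the type I error goes only from 0.152 to 0.130.

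**4. Coverage of the model as planned.** Simulation settings: REML MMRM, unstructured covariance, five visits, baseline covariate, normal data, correlation 0.7, placebo SD 40 mL, CBL-514 means moving linearly from −60 to −180 mL, 3,000 trials per setting (Monte Carlo error 0.4 points at 95%). Designs: 42/14 complete, and 50/25 with 8/11 random dropouts.

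Coverage (%) at Visit 7, pooled covariance with Satterthwaite df:

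| r | Difference, 42/14 | Difference, 50/25 with dropouts | CBL-514 arm, 42/14 | CBL-514 arm, 50/25 with dropouts |
|---|---|---|---|---|
| 0.5 | 84.9 | 86.8 | 98.8 | 99.3 |
| 1 | 94.9 | 94.8 | 95.4 | 94.8 |
| 1.5 | 98.2 | 97.3 | 93.5 | 92.2 |
| 2 | 99.3 | 98.9 | 93.4 | 91.5 |
| 3 | 99.7 | 99.5 | 92.5 | 89.9 |

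With `GROUP=treat` and Kenward-Roger, coverage of the difference is 94.2% to 95.5% throughout. Moving from Kenward-Roger to Satterthwaite makes the SE only 0.1% (42/14) to 1% (dropouts) smaller.

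**5. Only trials where the variance test fires.** With Levene's test run by visit (p < 0.05 at Visit 6 or 7) at 42/14, the SAP rule covers 85.4%, 98.2%, 99.5% and 99.7% at r = 0.5, 1.5, 2 and 3. `GROUP=treat` covers 95.9%, 94.7%, 95.5% and 94.8%.

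**6. Side check on the trigger.** Suppose the Levene code is run on all visits together while within-visit variances are equal. It then fires in 23% to 26% of trials with flat means, and in 27% to 99% with the moving means above as the SD falls from 120 to 40 mL. At Visit 7 alone it fires in 4% to 6%. A false trigger changes little in itself, because the remedy changes little.

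**The case against.** The strongest reply is that this is loose wording with small consequences. The sentence itself ends by saying that the option acts on degrees of freedom. The p-values carry the caveat "No claim can be made on these p-values based on this efficacy analysis as it is exploratory in nature", and the primary responder summary with Clopper-Pearson intervals is untouched. All magnitudes rest on assumed SD ratios. In the direction argued to be plausible, the between-arm interval is conservative. The clearly anti-conservative case needs a placebo SD twice that of CBL-514, for which no reason is offered. By-visit SDs for each arm will be tabulated, so a reader could see inequality and form an unadjusted interval.

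The remedy also has limits. A Levene trigger misses much moderate inequality. About 14 placebo completers would have to support 15 covariance parameters. The simulations used random dropout, whereas treatment visits can be cancelled for insufficient residual fat, which is related to outcome.

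These points bound the consequence and largely stand. They do not rescue the sentence: the SAP promises that all results are adjusted, and the standard errors are not. The Welch output is no substitute, since it compares arm means in PROC GLM and gives no MMRM interval at Visit 6 or 7. No listed table title mentions it, although the table shells were not available to check. Exploratory status limits what may be claimed from the results; it does not make a description of them accurate.

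**Conclusion.** The concern holds. If the variance test fires, the MMRM would be reported as adjusted for unequal variances while its standard errors remain pooled and its degrees of freedom do not reflect the inequality. That is certain from the text. The size depends on SD ratios the documents do not give. For ratios between 0.5 and 3, nominal 95% intervals for the difference cover from about 85% to 99.7%, and at ratios of 1.5 to 3 the CBL-514 arm's own intervals cover about 90% to 93.5%. The effect is confined to secondary, exploratory estimates. It should be corrected because the statement is wrong and the correction is cheap; it does not threaten the primary analysis.

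**What to change.** In SAP 16.3(c), replace the last sentence with text such as:

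> If arm variances differ (Levene's test run by visit, p < 0.05 at Visit 6 or Visit 7), the MMRM will use arm-specific covariance (`REPEATED visit / SUBJECT=usubjid TYPE=UN GROUP=treat`) with `DDFM=KR`. If it does not converge, the simpler Section 10 structures will be used, each with `GROUP=treat`. If per-visit regression is used, it will allow unequal arm variances.

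The 0.05 cutoff matches the SAP's normality code; any stated cutoff would do. If arm-specific covariance is not wanted, delete the sentence and state that the MMRM standard errors assume equal arm variances. That needs no programming.

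In 16.3(b), state that the main MMRM uses all observed values and is run whatever the normality test shows, with outlier exclusion only as a labelled sensitivity analysis under a stated rule. Align the condition in Section 10 with this.

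**Cost.** Wording, one REPEATED option when triggered and a by-visit Levene run; no new data. When triggered there are 30 covariance parameters instead of 15 (5 × 6/2 per arm), so non-convergence is possible. In simulation 29,999 of 30,000 such fits converged, but with normal data and random dropout. If variances are in fact equal, `GROUP=treat` widens the interval by 2% to 3%, and the trigger fires in only 9% to 11% of trials. At r = 1.5 it fires in 32% to 49%, so moderate inequality is often missed. Under the conditional rule, coverage is 94% to 97% for the difference and 93% to 96% for the CBL-514 arm at all ratios. Fitting arm-specific covariance from the outset avoids relying on the pre-test. A robust standard error is another route, not tested here.
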